2.0 Rationale and Specific Aims

The goal of this study is to assess whether using PTeye – a NIRAF detection modality – can reduce healthcare associated costs after parathyroid surgeries and improve patient outcomes. The specific aims of this study is to determine if PTeye is beneficial or not for (i) intraoperative identification of parathyroid tissues, (ii) improving efficiency of parathyroid surgeries, and (iii) minimizing risk of postsurgical complications.

By being able to quickly and definitively locate parathyroid glands while in the operating room, the duration of surgical procedure could be further reduced. In addition, the number of frozen section biopsy (or PTH aspirate) and associated costs can be minimized. Furthermore, repeat surgeries as a result of missing a diseased parathyroid gland at the time of the initial parathyroidectomy for hyperparathyroidism could potentially be avoided.

Primary Outcome Measure:

1. Number of frozen sections (or PTH aspirate) sent for analysis
 - a. Number of frozen sections (or PTH aspirate) sent for analysis during the procedure to confirm potential parathyroid tissue [Time Frame: Immediate. During PTx procedure.]

Secondary Outcome Measure:

1. Persistent hyperparathyroidism (Immediate)

- a. Failure of intra-operative parathyroid hormone (PTH) to normalize (defined as failure of PTH to drop > 50% of its baseline value at final intra-operative PTH assay and/or failure of PTH to drop < 65 pg/ml or 6.9 pmol/L). [Time Frame: During parathyroidectomy (PTx) procedure]
- 2. Persistent hyperparathyroidism or hypercalcemia (transient)
 - a. Elevated blood calcium levels (total blood calcium level > 10.5 mg/dL or 2.6 mmol/L) with/without elevated parathyroid hormone (PTH) (serum intact PTH > 65 pg/ml or 6.9 pmol/L) at first postoperative visit. [Time Frame: 5-14 days after PTx procedure]
- 3. Persistent hyperparathyroidism or hypercalcemia (failed parathyroidectomy)
 - a. If blood calcium with/without parathyroid hormone (PTH) has not normalized at 1st post-operative visit, calcium and/or PTH is subsequently measured as necessary. Patient is defined to have a failed parathyroidectomy if hypercalcemia/hyperparathyroidism (defined as total blood calcium level > 10.5 mg/dL or 2.6 mmol/L, with/without elevated serum intact PTH > 65 pg/ml or 6.9 pmol/L) persists at or after the 6th postoperative month. [Time Frame: 6 months after PTx procedure]
- 4. Overall number of parathyroid glands identified

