10.0 Statistical Considerations

Currently there are no comparable published randomized trials that have evaluated the effect of NIRAF detection for reducing intraoperative frozen section analysis (or PTH aspirate) during parathyroidectomies. Based on preliminary data obtained from a similar ongoing study at Vanderbilt University Medical Center over 123 patients, an 83% reduction in frozen section analysis was observed in the interventional group of 63 patients where NIRAF was used, compared to the control group of 60 patients where NIRAF was not used (unpublished). The mean frozen section analysis (FSA) obtained for the NIRAF group is 0.1 FSA/patient versus 0.6 FSA/patient obtained in the control group. Assuming, that an expected mean difference of 0.6 FSA/patient needs to be observed between the NIRAF and the control group, where the standard deviation of the enrolled study population is 0.8 (Standard Deviation obtained in VUMC study population is 0.78 FSA/patient), 47 patients would be required per group (for a 95% powered study). Since this study may involve patient follow-up for data up to 6 months after surgery, we will thus assume an approximate data attrition rate of 15%, thus requiring a recruitment of 55 patients per group. Therefore, a total of 110 patients (study and control arm) should be recruited per surgeon for this study at this study site. Overall, 110

patients need to be enrolled at this study site under a single surgeon to assess the impact of this technology.

Sample size	
2-side significance level	0.05
Power (1-beta)	0.95
Ratio of sample size, Control/NIRAF group	1
Expected mean in NIRAF group	0.7
Expected mean in Control group	0.1
Study population standard deviation	0.8
Result	
Sample Size - Control group	47
Sample Size - NIRAF group	47
Sample Size – Control group compensated for 15% attrition	55
Sample Size – NIRAF group compensated for 15% attrition	55
Total sample size	110

Analysis Plan:

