Continuous variables will be reported using medians and interquartile ranges (IQRs). Categorical variables will be reported using counts, percentages, and their 95% confidence intervals (CIs). Comparisons of the NIRAF and control parathyroidectomy groups for primary and secondary outcomes will be done using (a) 1-sided χ^2 or Fisher tests for categorical variables and (b) 2-tailed Student's t-test or Wilcoxon's test for continuous variables (depending on distribution of data). To analyze factors that influence the primary outcome assessed for this study, i.e., number of frozen sections specimens (or PTH aspirate) sent for analysis, a generalized linear mixed models will be used. The following variables will be considered as fixed effects for the study model: (i) nature of the intervention (NIRAF or control), (ii) age, (iii) BMI, (iv) number of intraoperative PTH assays, (v) number of diseased parathyroid glands seen, and (vi) type of parathyroid surgery (focused parathyroidectomy or bilateral neck exploration). The multivariate analysis based on this model will generate the respective odds ratios and their 95% CIs for the aforementioned factors that are being considered. A p-value ≤ 0.05 based on the statistical analysis for continuous/categorical variables under the primary and secondary outcomes measured in this study will be considered as significant.

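### The primary outcome is a count sized on a mean difference, but the only between-arm effect planned with a confidence interval is an undefined odds ratio from a model that includes intraoperative variables

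*Combined protocol and SAP*

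**What the plan says.** Section 2.0 defines the primary outcome as a per-patient count: "Number of frozen sections (or PTH aspirate) sent for analysis during the procedure to confirm potential parathyroid tissue". Section 10.0 sizes the trial on the mean of that count: "Assuming, that an expected mean difference of 0.6 FSA/patient needs to be observed between the NIRAF and the control group", with an SD of 0.8.

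The Analysis Plan in section 10.0 then offers three things that could apply to it:

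- A summary: "Continuous variables will be reported using medians and interquartile ranges (IQRs").
- A two-tailed arm comparison, by Student's t-test or Wilcoxon's "test for continuous variables (depending on distribution of data"). No estimate or interval is attached to either test.
- A model of what influences the primary outcome: "a generalized linear mixed models will be used". Its fixed effects begin "i) nature of the intervention (NIRAF or control), (ii) age, (iii) BMI" and continue "iv) number of intraoperative PTH assays, (v) number of diseased parathyroid glands seen", ending with type of surgery. Its output is stated as "The multivariate analysis based on this model will generate the respective odds ratios and their 95% CIs".

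The plan also promises 95% CIs on percentages for categorical variables. These are descriptive and are not an arm contrast for a count.

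**The concern.** Two features of the model matter if a reader takes its intervention term as the result of the trial.

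1. **Scale.** No distribution, link or cut-point is given, so the odds ratio is not defined for this outcome. Two analysts could follow the text and estimate different quantities. Neither would give frozen sections saved per patient, the quantity on which the trial is sized.
2. **Covariates.** The number of intraoperative PTH assays is secondary outcome 7. The number of diseased glands seen is closely related to the intraoperative count in secondary outcome 6. Both arise after randomisation, and the trial itself lists them as things the device may change. An intervention effect adjusted for them is not the total effect of the device. The plan does not say whether type of surgery means the approach planned or the one performed.

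What is at stake is the size of the benefit, not whether a difference is detected.

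**Working it through.** **The plan's own figure.** Inputs from section 10.0: difference 0.6, SD 0.8, two-sided 0.05, power 0.95.

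n per group = 2 × ((1.960 + 1.645) × 0.8 / 0.6)² = 46.2, rounded up to 47. This reproduces. With 15% attrition, 46.2 / 0.85 = 54.4, rounded up to 55. The sizing is on a difference of means, and nothing here disturbs it.

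**Assumptions for what follows.** The documents give no distribution, so I take Poisson or negative binomial (NB) counts. The NIRAF mean is 0.1. The control mean is 0.6 from the text of section 10.0, or 0.7 from its sample-size table read with the two arm labels swapped. As printed, the table gives 0.7 to NIRAF and 0.1 to control, which contradicts the text. A control variance near 1.0 applies only if the pilot SD of 0.78 is across both arms combined, which section 10.0 does not settle.

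**Formulas.**

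- P(zero) is exp(−m) for Poisson, and (k/(k+m))^k with k = m²/(v−m) for NB with mean m and variance v.
- The control median is 0 if at least 28 of 55 (24 of 47) patients have none (exact binomial tail). The NIRAF median is taken as 0, since P(any) is at most the mean, 0.1.
- The odds ratio for any frozen section uses P(zero) = 0.905 in the NIRAF arm (Poisson).
- Half-widths are means over 20,000 simulated trials of the unequal-variance 95% CI for the mean difference.

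| Control count | P(zero) | Both medians 0, n = 55 / 47 | Odds ratio, any vs none | CI half-width, n = 55 / 47 |
|---|---|---|---|---|
| Poisson 0.6 | 0.549 | 0.767 / 0.750 | 0.128 | 0.223 / 0.242 |
| NB 0.6, SD 0.8 | 0.559 | 0.813 / 0.794 | 0.134 | 0.230 / 0.249 |
| NB 0.6, variance 1.0 | 0.631 | 0.977 / 0.967 | 0.180 | 0.278 / 0.301 |
| Poisson 0.7 | 0.497 | 0.480 / 0.481 | 0.104 | 0.239 / 0.259 |
| NB 0.7, variance 1.0 | 0.558 | 0.809 / 0.791 | 0.133 | 0.279 / 0.303 |

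If the NIRAF count has variance 0.2, the half-widths rise to 0.289-0.290 (n = 55) and 0.313-0.314 (n = 47). Coverage is about 94-95% throughout. At the plan's SD of 0.8 in both arms, t × 0.8 × √(2/n) gives 0.302 (n = 55) and 0.328 (n = 47).

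**Summary display.** Both medians are 0 in about 48-98% of trials. In the same scenarios the upper quartile is higher in the control arm in about 96-100% of trials. A typical display would be 0 (0-1) against 0 (0-0): a visible difference without its mean size.

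**Scale.** An odds ratio of about 0.13 fits a saving of 0.5 (Poisson, control mean 0.6) or 0.6 (NB, control mean 0.7, variance 1.0). Conversely, a saving of 0.5 fits odds ratios of 0.12-0.18, the lower end arising with NIRAF variance 0.2.

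**Covariates (illustration only).** Suppose the assay count is Poisson, the device lowers it by d per patient, and each assay goes with an increase s in the log rate of frozen sections. Then the assay-adjusted rate ratio = total rate ratio × exp(d × (e^s − 1)).

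- d = 0: multiplier 1.00, no distortion.
- d = 0.5, s = 0.2: 1.12.
- d = 1, s = 0.4: 1.64, so 0.1/0.6 = 0.17 becomes 0.27.

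The documents give neither d nor s.

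**The case against.** The strongest reply is that the model is not the primary analysis. Section 10.0 introduces it as a way to study what influences the primary outcome, separately from the arm comparison, and nowhere calls the intervention odds ratio the device effect. That stands: intraoperative variables are acceptable in an exploratory model, and the covariate harm is conditional on how the term is read. It does not close the gap, because the intervention is still a term in that model and no other arm contrast for the count is promised an interval.

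A t-test could supply a mean difference with an interval. True, but the plan commits neither to that test nor to reporting the difference, and Wilcoxon's test does not estimate it.

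The scale illustration is modest. Savings of 0.5 and 0.6 differ by 0.1, less than the sampling half-width of 0.22-0.31. The firmer point is that the odds ratio is undefined for a count with no stated family, link or cut-point.

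A reader might infer that the planned summaries would hide the effect altogether. The median figures alone suggest it, but the quartiles show otherwise. A reader might also infer that choosing between the two tests by the data damages the trial. No harm from that choice has been shown here.

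**Conclusion.** The concern holds as a matter of estimation and should be fixed. The plan does not commit to a count-scale effect with a confidence interval, and the one between-arm effect it does commit to is undefined as written and adjusted for post-randomisation variables.

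It would be tempting to go further and say that the primary comparison is invalid, that the trial is mis-sized, or that the device effect will be biased by up to 64%. The documents support none of these. The test compares the arms directly and the stated sample size reproduces. The multiplier of 1.00-1.64 rests on assumed inputs in one direction, so it is neither a bound nor a prediction.

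The numerical ranges rest on the assumed count distributions and on reading the sample-size table with its arm labels swapped. The conclusions about scale and covariates rest on the text alone.

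**What to change.** - **Primary estimate.** Prespecify mean frozen sections (or PTH aspirates) per patient by arm, and the unadjusted mean difference with an unequal-variance or bootstrap 95% CI. Tabulate the counts (0, 1, 2, ...) by arm beside any median and IQR.
- **Model.** Replace the odds-ratio model with a log-link count regression with robust errors, reporting rate ratios with 95% CIs. Use no random effect if there is one surgeon, as section 10.0 states. That section also speaks of recruitment per surgeon and section 13.6 mentions a participating site, so confirm this. Keep odds ratios only for a labelled analysis of any versus no frozen section.
- **Covariates.** For the treatment effect, adjust only for pre-randomisation variables: age and BMI, and type of surgery only if the approach planned before randomisation is recorded. Label any model with intraoperative variables exploratory.

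Fixing the test in advance would be good practice but is not needed for this point.

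**Cost.** Plan wording and a little analysis time, with no change to sample size. Section 6.0 already has the count compiled for every patient. Planned surgical approach would be one extra data item.

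**Downsides.** The mean is sensitive to a few high counts. About 5 events are expected in the NIRAF arm (0.1 × 47 = 4.7; 0.1 × 55 = 5.5), so the rate-ratio interval will be wide. The ratio cannot be estimated if that arm has no events: exp(−0.1n) = 0.4% (n = 55) or 0.9% (n = 47) under Poisson, and 0.933^n = 2.2% or 3.8% with NIRAF variance 0.2. The mean difference can still be estimated then.

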 - a. Overall number of parathyroid glands identified (Experimental Group: Glands identified with naked eye + NIRAF; Control Group: Glands identified with naked eye) [Time Frame: Immediate. During PTx procedure.]
- 5. Number of parathyroid glands identified with NIRAF
 - a. Number of parathyroid glands identified with NIRAF, which was not seen with surgeon's naked eye [Time Frame: Immediate. During PTx procedure.]
- 6. Number of diseased parathyroid glands identified versus preoperatively localized glands
 - a. Number of diseased parathyroid glands identified intra-operatively versus glands localized preoperatively using sestamibi, CT or ultrasound [Time Frame: Preoperative to immediate during PTx procedure.]
- 7. Number of intra-operative parathyroid hormone (PTH) assays sent
 - a. Number of intra-operative parathyroid hormone assays sent during the procedure [Time Frame: Immediate. During PTx procedure.]
- 8. Duration taken to identify first parathyroid gland
 - a. Duration taken to identify 1st parathyroid gland in PTx procedure – timed from skin incision to finding PG. [Time Frame: Immediate. During PTx procedure.]
- 9. Duration taken to identify last parathyroid gland
 - a. Duration taken to identify last parathyroid gland in PTx procedure – timed from skin incision to finding the last PG. [Time Frame: Immediate. During PTx procedure.]
- 10. Duration of parathyroidectomy (PTx) procedure
 - a. Duration of PTx procedure – timed from skin incision until the surgeon notifies the anesthesia team to awaken the patient [Time Frame: Immediate. During PTx procedure.]
- 11. Duration taken for intraoperative parathyroid hormone (PTH) to normalize
 - a. Time taken for PTH to attain cure criteria or normalize - timed from skin incision until the PTH levels drops > 50% of its baseline value and/or PTH drops < 65 pg/ml or 6.9 pmol/L. [Time Frame: Immediate. During PTx procedure.]
- 12. Number of nights spent in the hospital after parathyroidectomy
 - a. Number of nights spent for postoperative recovery in the hospital after the surgical procedure. [Time Frame: 0-72 hours after PTx procedure.]
- 13. Number of 'false positive' tissues excised by surgeon
 - a. Number of tissues that were excised by surgeon assumed to be parathyroid tissue, but is later validated as nonparathyroid tissue (false positive) by histology [Time Frame: Immediate to 10 days after PTx procedure.]
- 14. Number of doctor visits/emergency department visits or hospital admissions

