- a. Number of doctor visits/emergency department visits or hospital admissions due to persistent hypercalcemia and/or associated symptoms after parathyroidectomy procedure [Time Frame: Up to 6 months after PTx procedure.]
15. Number of patients who have had repeat parathyroidectomy (PTx) procedure
 - a. Number of patients with repeat PTx procedure performed after the current procedure [Time Frame: 6 - 12 months after PTx procedure.]

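### Secondary outcomes get the same p ≤ 0.05 significance label as the primary, with no multiplicity control: for 14 comparable outcomes, up to about 51% chance of a false significant result and 37% of a device-favouring one

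*Combined protocol and SAP*

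**What the plan says.** Section 2.0 (Rationale and Specific Aims) names one primary outcome, the number of frozen sections or PTH aspirates sent. It then numbers its secondary outcomes up to "15. Number of patients who have had repeat parathyroidectomy (PTx) procedure". The same section sets out what the trial is for: "The specific aims of this study is to determine if PTeye is beneficial or not", with respect to identification of parathyroid tissue, surgical efficiency and postsurgical complications.

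The Analysis Plan in section 10.0 specifies "Comparisons of the NIRAF and control parathyroidectomy groups for primary and secondary outcomes", using "1-sided χ^2 or Fisher tests for categorical variables" and "2-tailed Student's t-test or Wilcoxon's test for continuous variables". It closes with the decision rule, under which any result at or below the 0.05 threshold, for either type of variable, "under the primary and secondary outcomes measured in this study will be considered as significant".

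Neither section contains a multiplicity adjustment, a hierarchy, a gatekeeping step or an exploratory label. The sample size calculation in section 10.0 covers the primary outcome only.

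**The concern.** This is a stated rule, not an omitted detail. It gives every secondary outcome the threshold and the label that the primary has. With many outcomes tested this way, chance alone is likely to produce some result that the plan calls significant.

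The secondary outcomes matter to the trial's purpose. The primary counts confirmatory specimens and does not directly measure complications, so that aim has to draw on secondary outcomes. Efficiency also has several candidates, including assay counts, durations and hospital nights. The plan does not say which outcome answers which aim. A report that follows the plan could therefore highlight one significant secondary result without telling the reader how many chances there were to find one.

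**Working it through.** **The plan's own figure.** The only design figure is for the primary: difference 0.6, SD 0.8, two-sided 0.05, power 0.95. Then n = 2 × (1.960 + 1.645)² × 0.8² / 0.6² = 46.2, or 47 per group, as stated. The stated 55 follows from 47 × 1.15 = 54.05, rounded up (dividing by 0.85 would give 56). The plan states no error rate over the secondary outcomes, so there is none to reproduce.

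**Number of comparisons.** Section 2.0 lists 15 secondary outcomes. Outcome 5 is defined as "Number of parathyroid glands identified with NIRAF, which was not seen with surgeon's naked eye". Section 6.0 says the device is not used in the control arm, so this outcome has no control value. That leaves 14.

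**Any false significant result, all null, independent tests.** Each test has size 0.05, whether one- or two-sided.
- 14 outcomes: 1 − 0.95¹⁴ = 0.512.
- All 15, for comparison: 1 − 0.95¹⁵ = 0.537.
- Expected number of false positives over 14: 14 × 0.05 = 0.70.

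**At least one false result favouring the device.** The plan assigns no test to individual outcomes and gives no direction for the one-sided tests. I read outcomes 1, 2, 3 and 15 as categorical (size 0.05, assumed directed toward the device). I read the other 10 as counts or continuous measures (two-tailed, so 0.025 in the device's favour).
- 1 − 0.95⁴ × 0.975¹⁰ = 1 − 0.8145 × 0.7763 = 0.368.
- All 14 tested two-sided: 1 − 0.975¹⁴ = 0.298.
- Categorical tests almost never reject: 1 − 0.975¹⁰ = 0.224.

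**Correlation.** The documents give no correlations. I assumed equicorrelated normal test statistics for the 14 outcomes, all oriented so that positive favours the device (300,000 simulated trials):

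| Assumed correlation | Any false significant result | Device-favouring |
|---|---|---|
| 0 | 51% | 37% |
| 0.2 | 48% | 31% |
| 0.3 | 44% | 27% |
| 0.5 | 36% | 21% |
| 0.7 | 26% | 16% |

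**Rare events.** The exact size of a one-sided Fisher test at 47 to 55 per arm is about 0.1–0.2% at an assumed 2% event rate, 1.0–1.3% at 5% and 2.3–2.6% at 10%. Section 1.0 puts failed parathyroidectomy at 5–10%. If Fisher's test is the one chosen, such an outcome contributes well under its nominal 5%.

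**Benchmark.** The primary's two-sided 0.05 design allows a 2.5% chance of a false result in the device's favour.

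**The case against.** The strongest objections concern size and consequence.

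- **Direction.** A reader might infer from the 51% that there is an even chance of a false benefit claim. The documents do not support that. The continuous comparisons are two-tailed, so half of their false positives would favour control. The device-favouring figure is at most about 37%.
- **Independence.** It is not realistic here. Outcomes 8 to 11 are all timed from skin incision, outcomes 1 to 3 are linked definitions of persistent disease, and 14 and 15 are consequences of it. This stands, and the figures above are upper values. Even so, the lowest correlated scenario, 16%, is several times 2.5%.
- **The primary.** A reader might also infer that the primary's error rate is inflated, or that the plan lets a significant secondary outcome rescue a failed primary. Neither follows. There is one primary outcome, the secondary tests do not alter its alpha, and the rule only says when a p-value is called significant. It does not say what that establishes about the device.
- **Stakes.** This is a single-centre, minimal-risk study of an FDA-cleared device, and no regulatory claim is described. That lowers the priority.
- **Convention.** Secondary outcomes are often understood as exploratory. This plan does not say so, and its wording treats them as it treats the primary.

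The objections reduce the size and urgency of the point. They do not remove it.

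**Conclusion.** The point holds as a cheap improvement. The plan calls any of 14 comparable secondary outcomes significant at p ≤ 0.05, on the same footing as the primary and without multiplicity control. If all are null and independent, the chance of at least one false significant result is up to about 51%, and of at least one device-favouring result up to about 37%.

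The 37% rests on reading four outcomes as categorical and on one-sided tests directed toward the device. Across assumed correlations of 0.3 to 0.7 the device-favouring figure is about 27% down to 16%. With independent outcomes but categorical tests that almost never reject, it is about 22%. The conclusion concerns the secondary claims only.

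**What to change.** In the Analysis Plan, limit the p ≤ 0.05 significance rule to the primary outcome. State that all secondary outcomes are supportive and will be reported with effect estimates and two-sided 95% confidence intervals, without the significant label.

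If confirmatory secondary claims are wanted, name a short list in advance and test it with Holm's procedure, two-sided, only if the primary is met. Choose the list with power in mind. For failed parathyroidectomy in a list of three, the first Holm threshold is 0.05/3 = 0.0167. With a two-sided Fisher test and 47 to 55 per arm, power would be about 1–2% at a 5% control rate and 19–31% at 10%, even if the device arm had no failures at all.

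The basic change is about one sentence and needs no extra patients or data. Its cost is that an isolated secondary p-value can no longer be called significant. Since the rule would then rest on the primary alone, the plan should also say whether the two-group test or the mixed model decides it, because section 10.0 describes both.
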